6.2.7 Analysis of other efficacy variables

The analysis of the other variables will be based on the ITT analysis set and ITT data scope, including events as adjudicated by the ICAC or reported by investigators if not being adjudicated. These analyses will be considered exploratory.

The analysis methods will be similar to those described for the primary efficacy outcome except for patient reported outcomes.

For EQ-5D and WIQ, the change from baseline of the mobility domain of EQ-5D and each domain of WIQ (pain [PAD specific question and Q1 of differential diagnosis], distance, speed, stair climbing) will be analyzed using an ANCOVA model with baseline value as a covariate and treatment as the only fixed effect. Baseline is the last measurement prior to or at randomization.

For limb hemodynamics (ABI and TBI separately), the changes from baseline will be analyzed using an ANCOVA model with baseline value as a covariate and treatment as the only fixed effect. Since the ABI and TBI is expected to improve after qualifying revascularization and decrease gradually over time, baseline value is defined as the measurement at month 1 visit.

Summary statistics of EQ-5D, WIQ and ABI and TBI actual and change from baseline values will also be provided by visit.

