### **9.7      Other procedures and variables**

#### **9.7.1      European Quality of Life-5 Dimensions Questionnaire - amended**

For the quality of life assessment the European Quality of Life-5 Dimensions Questionnaire (EQ-5D) will be used as a standardized measure of health outcomes. The assessment is

 Paragraph was added with Protocol Amendment 4 (change no. 19)

applicable to a wide range of health conditions and treatments and it provides a simple descriptive profile and a single index value for health status. The EQ-5D is primarily designed for self-completion by patients.

The EQ-5D will be administered at the randomization visit, and subsequently at each on-site visit.

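### SAP 6.2.7 fits an ANCOVA with no visit, within-patient covariance or missing-data rule to the repeatedly measured EQ-5D, WIQ, ABI and TBI; a repeated-measures model with named visits is a cheap improvement (minor)

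*SAP*

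**What the plan says.** For the questionnaires, SAP 6.2.7 states that "the change from baseline of the mobility domain of EQ-5D and each domain of WIQ" "will be analyzed using an ANCOVA model with baseline value as a covariate and treatment as the only fixed effect". Their baseline is set by "Baseline is the last measurement prior to or at randomization". For the limb measurements it says "For limb hemodynamics (ABI and TBI separately), the changes from baseline will be analyzed using an ANCOVA model", again with baseline and treatment only, but here "baseline value is defined as the measurement at month 1 visit". Visits appear once in the section, for descriptive output: "Summary statistics of EQ-5D, WIQ and ABI and TBI actual and change from baseline values will also be provided by visit". Of all the other efficacy variables it says "These analyses will be considered exploratory".

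The measurements are repeated. Protocol 9.7.1 states: "The EQ-5D will be administered at the randomization visit, and subsequently at each on-site visit". Protocol 9.7.2 has the same timing for the WIQ, and 9.2.1.3 and 9.2.1.4 place ABI/TBI at every treatment-phase visit and at the end-of-treatment (EOT) visit. Protocol section 5 sets on-site visits at months 1, 3, 6 and 12 and then every 6 months.

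No other section fills the gap. Protocol 10.3.3.2 exempts the patient-reported outcomes from the primary method without giving another. SAP 4.3 deals with event dates. The imputation and tipping-point work in SAP 6.2.10 and Appendix C covers the primary endpoint only. SAP 6.2.8 lists further ABI/TBI explorations but gives no model for them.

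**The concern.** An ANCOVA with one baseline and one treatment term takes one change value per patient. These outcomes supply several, and the section does not say which one enters or how several would be combined. Two programmers could follow the text and produce different analyses.

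The two readings carry different risks. Run visit by visit, each fit is a complete-case analysis that discards what is known from earlier visits, and nobody has said which visit carries the message. Run on all visits stacked together, repeated values from one patient would count as independent, and standard errors would be too small. What is at stake is how far the treatment comparisons on walking, mobility and limb perfusion can be trusted. The primary result and the tested secondary hierarchy are not involved.

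**Working it through.** The plan gives no sample size, standard deviation or power for these scales, so it has no figure of its own to reproduce. The 1,015-event target does not depend on them.

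**1. Values per patient.** Minimum follow-up is 24 months (SAP 4.6) and maximum about 42 months (protocol synopsis). I take the last scheduled visit as the EOT visit.
- 24 months: months 1, 3, 6, 12, 18, 24 = 6 values.
- 42 months: the same plus months 30, 36, 42 = 9 values.
- ABI/TBI use month 1 as baseline, so they have 6 − 1 = 5 to 9 − 1 = 8 change values.

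**2. Number of comparisons if fitted per visit.** The scales are EQ-5D mobility (1), WIQ pain, distance, speed and stair climbing (4), ABI and TBI (2), so 7 in all.
- To month 24: 5 × 6 + 2 × 5 = 40.
- To month 42: 5 × 9 + 2 × 8 = 61.

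None is named as the lead.

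**3. Per-visit reading.**
- Error rate: null simulation of a single-visit ANCOVA (2,000 runs, 400 patients) gave a two-sided error of 4.4% to 5.5% in every setting tried. The standard errors are valid.
- Planned missingness: SAP 4.6 assumes 1.5% per year lost or dying of non-CV causes, so 2 × 1.5% = 3% by month 24. CV deaths add part of the 7.5% per year control-arm composite rate. Follow-up by phone or through a third party (Protocol 6.3.1) could add missing measurements, but no figure is given.
- Planned thinning: accrual of 15%, 30% and 55% per half-year means all patients can reach month 24, 15% + 30% = 45% can reach month 30, and 15% can reach month 36, before losses. Much of the later reduction is therefore administrative.
- Bias: simulations assumed about 20% missing at month 24, a true effect of 0.100 SD, and missingness depending on earlier values equally in both arms. Complete-case ANCOVA gave 0.097 to 0.098 and a likelihood method using all visits gave 0.099 to 0.100. The likelihood method gained 2% to 3% in precision. When the dependence differs by arm, complete-case estimates are biased, with direction and size set by the dependence assumed.

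**4. Pooled reading.** The documents give no within-patient correlation ρ, so I assume 0.3 to 0.7 under compound symmetry. After baseline adjustment the remaining correlation is r = (ρ − ρ²)/(1 − ρ²) = ρ/(1 + ρ), which is 0.231 at ρ = 0.3 and 0.412 at ρ = 0.7. With m values per patient the design effect is 1 + (m − 1)r. The ratio of true to reported standard error is its square root, and the actual two-sided error is 2[1 − Φ(1.96/ratio)].

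For m = 6: 1 + 5 × 0.231 = 2.15, ratio 1.47, error 18.2%; and 1 + 5 × 0.412 = 3.06, ratio 1.75, error 26.2%.

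| m | ratio, ρ = 0.3 | error | ratio, ρ = 0.7 | error |
|---|---|---|---|---|
| 5 | 1.39 | 15.8% | 1.63 | 22.8% |
| 6 | 1.47 | 18.2% | 1.75 | 26.2% |
| 8 | 1.62 | 22.6% | 1.97 | 32.0% |
| 9 | 1.69 | 24.5% | 2.07 | 34.4% |

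Simulation for m = 6 gave 18.3% and 25.0%, and the other rows agree to about 2 points. The rows for 8 and 9 values need close to the full 42 months, which few patients can reach on the planned accrual, so m = 6 is the fairer illustration.

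**The case against.** The strongest reply is that pooling was never meant. A conventional ANCOVA takes one value per patient. The word *also* in the by-visit sentence fits models run per visit. SAP 6.2.8 uses frailty models and robust standard errors where it analyses several events per patient, so its authors knew the issue. Programming instructions sit in a separate output specification (SAP section 1) that is not available here. This stands: per-visit fits are the likelier intention, although the SAP does not say so. A reader might infer that the plan yields invalid p-values for these outcomes; the text does not support that.

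A reader might also infer that per-visit fits would be materially biased. That needs substantial missingness that depends on earlier values differently in the two arms. The documents give neither. They plan low loss to follow-up, and Protocol 6.3.1 expects patients who stop study drug to keep attending visits. Unequal missingness is possible, since the trial hypothesises fewer vascular events on rivaroxaban, but its size is unknown.

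Nor are these the only planned looks at limb haemodynamics, because SAP 6.2.8 adds more.

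Finally, it can be said that naming a visit for the existing ANCOVA would be enough. It would remove the ambiguity, but it would still discard earlier values and rest on the stronger missing-data assumption.

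**Conclusion.** The point holds as a minor one. SAP 6.2.7 leaves visit, time effect, covariance and missing data unspecified for 7 repeatedly measured scales. On the likelier reading, tests keep their nominal level; the costs are unused data, an open choice among some 40 comparisons by month 24, and exposure to bias only if missingness depends on earlier values differently by arm. On the less likely pooled reading, error would be roughly 18% to 26% for 6 values. That range rests on the assumed ρ of 0.3 to 0.7, compound symmetry and 6 values from every patient. A higher figure for 6 values would need stronger correlation than assumed, for example follow-up values more alike than they are like baseline, and the documents give no basis for it. The analyses are exploratory, so no confirmatory claim and no allocated alpha is affected.

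**What to change.** In SAP 6.2.7, replace the ANCOVA by a mixed model for repeated measures with treatment, visit, treatment by visit, baseline, baseline by visit and an unstructured within-patient covariance. This uses every visit and is valid under a weaker missing-data assumption than complete-case fits. Name the visit or visits at which the treatment contrast is reported. Months 12 and 24 are one sensible choice, since both lie within the planned minimum follow-up.

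The mixed model treats values after death as missing at random, so add a sensitivity analysis for EQ-5D and WIQ that handles deaths explicitly, for example by assigning them the worst value.

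The cost is a few sentences in the SAP and a standard SAS procedure. No new data are needed, and the downside is slightly more analysis work.

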### **7.3 Treatment assignment - amended**

Allocation to treatment arms will be done centrally by IxRS. Allocation will be performed in a ratio of 1:1 to each study treatment arm and will be stratified in one of 3 strata by:

- surgical revascularization,
- endovascular revascularization with clopidogrel,
- endovascular revascularization without clopidogrel.

Given potential differences in natural history resulting from procedure type, variation in medical practice, and concomitant therapy that may affect treatment outcome.

The clopidogrel use defining the randomization strata refers to actual clopidogrel use, at randomization, as adjunct treatment for the qualifying revascularization. Specific procedures for treatment assignment through the IxRS will be described in the IxRS manual.

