- To evaluate whether rivaroxaban added to ASA is superior to ASA alone in reducing the risk of venous thromboembolic (VTE) events.

The primary safety objective of the study is:

- To evaluate the overall safety and tolerability of rivaroxaban added to ASA compared to ASA alone.

3. Study Design

This study is an international multicenter, randomized, placebo-controlled, double-blind, event-driven phase 3 study.

Following provision of informed consent, subjects who fulfill all inclusion criteria and meet none of the exclusion criteria will be treated with ASA 100 mg once daily (od) and randomly allocated by an interactive voice/web response system (IxRS) in a ratio of 1:1 to additional treatment with either rivaroxaban 2.5 mg or placebo twice daily (bid). The randomization will be stratified by type of procedure and use of clopidogrel (i.e., (i) surgical vs. (ii) endovascular with clopidogrel vs. (iii) endovascular without clopidogrel). Treatments will be balanced within a country for each stratum by block randomization. Randomization and study treatment should commence as soon as possible but no later than 10 days after a successful qualifying revascularization procedure and once hemostasis has been assured. All randomized subjects will receive study medication (either rivaroxaban or placebo) and study ASA in a sufficient quantity until the next scheduled on-site visit and detailed instructions for its administration.

The study is event-driven, and thus, all subjects will be treated (or followed-up in the case of permanent discontinuation of study medication) until the end of treatment (EOT) visit. It is estimated that approximately 6,500 subjects (3,250 per treatment group) are needed to be enrolled in order to have 1,015 subjects experiencing a confirmed primary efficacy outcome event. Due to the event-driven study design, no firm treatment duration can be stipulated for an individual subject. The estimated maximum treatment period for an individual subject is approximately 42 months, and the mean treatment duration is expected to be approximately 30 months. However, this duration may vary depending on the recruitment rate as well as the primary event rate.

Statistical Analysis Plan

Protocol No.: **BAY 59-7939 / 17454**

[figure not shown]
Page: 8 of 36

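### The exploratory ANCOVAs for EQ-5D mobility, WIQ, ABI and TBI leave out the randomisation stratum, so their standard errors may be slightly too large

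*SAP*

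**What the plan says.** SAP 6.2.7 covers the other efficacy variables. For the questionnaires, the outcome modelled is "the change from baseline of the mobility domain of EQ-5D and each domain of WIQ", and it "will be analyzed using an ANCOVA model with baseline value as a covariate and treatment as the only fixed effect". A separate paragraph sets the same model for ABI and for TBI. The section also promises by-visit description: "Summary statistics of EQ-5D, WIQ and ABI and TBI actual and change from baseline values will also be provided by visit". On the status of all this it is explicit: "These analyses will be considered exploratory".

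On the design side, SAP section 3 says: "The randomization will be stratified by type of procedure and use of clopidogrel". There are three strata: surgical, endovascular with clopidogrel, and endovascular without clopidogrel. Protocol 7.3 gives the reason: "Given potential differences in natural history resulting from procedure type, variation in medical practice, and concomitant therapy that may affect treatment outcome".

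The main time-to-event analyses carry these strata, as assigned by IxRS: the primary log-rank test and Cox model (SAP 6.2.5), the secondary outcomes (6.2.6 and Table 1), the landmark analyses (6.2.8) and the bleeding analyses (6.4.5). The Weibull model behind the tipping-point analysis also adjusts for them (6.2.10 and Appendix C).

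**The concern.** When allocation is balanced within strata, differences between strata cannot contribute to the difference between arms. A model without the stratum still counts those differences as residual noise. Its standard error then describes an unstratified trial, and it overstates the real variability of the estimate whenever the strata predict the outcome after baseline is accounted for.

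Procedure type could plausibly predict walking ability or limb haemodynamics. SAP 6.2.8 itself plans to look at ABI and TBI change separately for endovascular and surgical patients. Yet 6.2.7 gives no reason for omitting the stratum. At stake is a little precision on the patient-reported and haemodynamic comparisons: confidence intervals somewhat wider, and p-values somewhat larger, than the design warrants.

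**Working it through.** The documents give no standard deviation, effect size or power for EQ-5D, WIQ, ABI or TBI, so there is no stated figure to reproduce. The check has three parts.

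**1. Size of the effect on the standard error.** Let R² be the share of residual variance, after baseline and treatment, that the strata explain. R² is an assumption; the documents give none.

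- Reduction in standard error from adding the stratum: 1 − √(1 − R²).
- Actual two-sided error rate of a nominal 5% test without the stratum: 2Φ(−1.96/√(1 − R²)), where Φ is the standard normal distribution function. This follows because the estimate varies as if the stratum were fitted, while its standard error is computed as if it were not.

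| Assumed R² | SE reduction if stratum added | SE excess if omitted | Effective critical value | Actual two-sided error |
|---|---|---|---|---|
| 0.01 | 0.5% | 0.5% | 1.970 | 0.049 |
| 0.02 | 1.0% | 1.0% | 1.980 | 0.048 |
| 0.05 | 2.5% | 2.6% | 2.011 | 0.044 |
| 0.10 | 5.1% | 5.4% | 2.066 | 0.039 |

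**2. Simulation under no treatment effect.** Inputs, all assumed: 1,000 patients, three equally likely strata, 1:1 allocation balanced within stratum, 3,000 runs per scenario, and an ordinal item with 3 or 5 levels analysed as a numeric change score with baseline as covariate. Strata shift the latent score by 0, 0.2 or 0.5 between adjacent strata.

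| Levels | Stratum shift | Type I error without / with stratum | Mean SE without / with stratum |
|---|---|---|---|
| 3 | 0 | 0.046 / 0.046 | 0.03365 / 0.03365 |
| 3 | 0.2 | 0.045 / 0.050 | 0.03387 / 0.03339 |
| 3 | 0.5 | 0.037 / 0.052 | 0.03475 / 0.03220 |
| 5 | 0 | 0.050 / 0.050 | 0.06086 / 0.06086 |
| 5 | 0.2 | 0.046 / 0.051 | 0.06133 / 0.06036 |
| 5 | 0.5 | 0.035 / 0.049 | 0.06310 / 0.05797 |

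The Monte Carlo standard error of a 5% rate is √(0.05 × 0.95/3,000) = 0.004. The mean treatment estimate is about zero in every scenario, at most 0.0011 in absolute value, with or without the stratum.

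The standard errors imply R² through 1 − (SE with/SE without)². For the 0.2 shift this is 1 − (0.03339/0.03387)² = 2.8% and 1 − (0.06036/0.06133)² = 3.1%, inside the assumed range. For the 0.5 shift it is 1 − (0.03220/0.03475)² = 14.1% and 1 − (0.05797/0.06310)² = 15.6%. That lies beyond the range, and the standard error falls by 7.3% and 8.1%. With no stratum effect the two models agree.

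**3. How much of the stratum effect baseline already absorbs.** For ABI and TBI, SAP 6.2.7 takes the month 1 visit as baseline, after the procedure, so part of any procedure-related difference is already in the covariate. For EQ-5D and WIQ, baseline is the last value at or before randomisation, and Protocol 9.2.1.2 asks for answers that reflect the period before the qualifying procedure. Baseline therefore cannot absorb a difference in recovery by procedure type. Any gain is more likely for the questionnaires than for the haemodynamic measures.

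**The case against.** The strongest reply is that nothing depends on this. The analyses are exploratory and outside the testing sequence of SAP 6.2.6. Omitting the stratum errs on the conservative side, and the gain rests on an R² that the documents do not supply. SAP 6.2.8 already examines ABI and TBI by procedure type, and 6.2.9 allows further analyses of other endpoints by stratum. All of this stands, and it is why the point is minor. It does not justify the omission, because these ANCOVAs are the only between-arm models specified for these outcomes and the stratum is already recorded in IxRS.

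A reader might infer more in three ways, and the documents do not support any of them.

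- **That the strata are used in every other analysis.** They are not. SAP 6.2.10 includes an unstratified Cox model as a sensitivity analysis. In 6.2.8 the exploratory subgroup models are unstratified and the frailty model has treatment as its only covariate. Subgroups defined by procedure or clopidogrel are also unstratified (6.2.9 and Table 1, note 4). Some of these have evident reasons, but the ANCOVAs are not a lone exception.
- **That the EQ-5D index is never analysed.** Protocol 9.7.1 says of the instrument that "it provides a simple descriptive profile and a single index value for health status", and 6.2.7 names a model only for mobility. But by-visit EQ-5D summaries are planned without saying whether the index is included, and the table specifications are in a separate document. The protocol does not commit to comparing the index between arms.
- **That ANCOVA on the mobility item is invalid.** The documents give neither the EQ-5D version nor the number of levels. With 3 or 5 levels assumed, type I error without the stratum was 0.035 to 0.050. A mean change on an ordinal code is harder to interpret, but choosing another model is a preference.

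**Conclusion.** The point holds as a small, free improvement. The ANCOVAs in SAP 6.2.7 omit a factor that the trial randomises by and that its main models use. If the strata explain 1% to 10% of residual variance beyond baseline, adding them lowers the standard error by about 0.5% to 5%, and a nominal 5% test without them has an actual level of about 0.049 down to 0.039. If the strata explain nothing beyond baseline, nothing is lost either way. Those percentages depend entirely on the assumed R². The direction does not: omission costs precision where the strata matter, causes no bias and does not inflate the error rate. The primary, secondary and safety conclusions are untouched.

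**What to change.** In SAP 6.2.7, in both ANCOVA paragraphs (EQ-5D mobility and WIQ; ABI and TBI), add the randomisation stratum per IxRS assignment as a fixed effect with three levels: surgical, endovascular with clopidogrel, and endovascular without clopidogrel. Baseline stays as the covariate, and treatment remains the effect of interest.

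The cost is one sentence in each paragraph and one class variable in the code. No new data are needed, and two extra parameters are negligible in a trial of about 6,500 patients.

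Two optional additions would help readers but correct no error: a supporting ordinal analysis of EQ-5D mobility, and a statement of whether the EQ-5D index will be derived and compared between arms. The index would also need a stated scoring method, which the documents do not give.

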6.2.8 Exploratory analysis

Exploratory analysis of the individual components of the primary and secondary efficacy outcomes will be analyzed similarly to the primary efficacy outcome. Composite outcomes major adverse cardiac events (MACE, ie. CV death, MI and ischemic stroke) and major adverse limb events (MALE, i.e. ALI and major amputation due to a vascular etiology) will be analyzed similarly to the primary efficacy outcome.

To account for the multiple components of the primary efficacy endpoint, all event analysis will be evaluated in ITT data scopes and on-treatment data scopes by fitting frailty model with gamma distribution of the shared frailty terms as an extension of the Cox accounting for correlation of the events within a subject (see [Hougaard, 2000](#); [Wienke, 2011](#); [Austin, 2017](#)), with treatment as the only covariate. In addition, model with log-normal distribution of the shared frailty terms will be fitted. Another extension of the Cox model is the Andersen-Gill model, which assumes that each recurrence is an independent event ([Andersen, 1982](#)). To account for the intra-subject correlation, models with robust standard error estimator will be fitted according to Lin's method ([Lin et al. 2000](#)).

The primary efficacy endpoint will be explored for the following subgroups

Qualifying endovascular techniques

- Balloon angioplasty (drug-coated and not coated), yes/no

Statistical Analysis Plan

Protocol No.: **BAY 59-7939 / 17454**

Page: 23 of 36

- Angioplasty with stent (bare metal, drug-coated, covered) yes/no
- Atherectomy
- Thrombolysis
- Time from qualifying revascularization procedure to randomization (<median; \geq median)
- History of lower limb amputation
 - Major ischemic amputation with or without other amputation
 - Minor ischemic amputation with or without non-ischemic amputation
 - Nonischemic amputation only
 - No amputation

The frequency will be presented descriptively (and with forest plots). The hazard ratio for the treatment effect will be estimated separately within each level of a subgroup using the Cox proportional hazards model without stratification.

The following variable will also be explored:

- Time from randomization to the first occurrence of MI types
- Any revascularization after randomization regardless of the side as reported by the investigator
- Any index leg revascularization as reported by the investigator

In addition, ABI and TBI will be further explored to understand the effect of natural history and drug effect on hemodynamics. Examples include:

- Change in ABI and TBI post randomization excluding values after subsequent revascularization by subgroup (endovascular versus surgical)
- Change in ABI and TBI post randomization in patients with subsequent intervention versus those who do not undergo subsequent intervention

To explore the robustness of the treatment effect over time, landmark analyses will be performed for the primary endpoint according to landmark periods of randomization to 3-month, 3-month to 1-year and 1-year to the end of treatment phase and randomization to 6-month, 6-month to 1 year and 1-year to end of treatment phase ([Van Houwelingen 2007](#)). Additional time point after 1-year may be added depending on the actual study duration. For each landmark period, the hazard ratio will be estimated using a Cox PH model stratified by type of procedure and use of clopidogrel (per IxRS assignment) with treatment as the only covariate, the corresponding 95% CI will be provided, and Kaplan-Meier (KM) plot of cumulative risk will be generated, respectively. The hazard ratio will also be calculated for the two main components (MACE versus MALE) of the primary endpoint.

